### A3a. Financial Conflict of Interest

Does any member of study personnel (Investigator (including investigator's spouse and/or dependent children)) that are involved in the design, conduct, or reporting of the research have a Significant Financial Interest (SFI) that would reasonably appear to be affected by the research for which funding is sought and/or associated with an entity/business that would reasonably appear to be affected by the research?

No

**A5. Funding Source:**

Organization: VA CENTRAL OFFICE, RR&D

**A6b. Research conducted outside of the United States:**

Country:  
Facility/Institution:  
Contact/Investigator:

Phone Number:

If documentation of assurances has not been sent to the Office of Research, please explain:

**A7. Research Category:**

**A8. Therapeutic Intent**

Does this trial have therapeutic intent?

No

**Section B: Exempt Request**

**B. Exempt From IRB Review**

Not Applicable

## **Section C: Background Information**

Approximately 18-22% of Operation Enduring Freedom/Operation Iraqi Freedom/ Operation New Dawn (OEF/OIF/OND) Veterans have been diagnosed with posttraumatic stress disorder (PTSD), and 15-30% of Veterans report mild traumatic brain injury (mTBI). The effects of mTBI and PTSD have been evident since military personnel first came home and continue to be difficult to eradicate. At 3-4 months post-deployment, OIF Veterans with mild TBI (mTBI) were more likely to endorse PTSD symptoms than those without mTBI. The comorbidity may be long-lasting, or at least recurrent, as TBI-related symptoms were strongly associated with traumatic stress five years after injury. In an examination of factors associated with postconcussive symptoms, PTSD was a strong factor. In active duty marines, mTBI during deployment predicted PTSD after deployment, and in a study of OEF-OIF-OND Veterans, 57.3% of those with mTBI had PTSD.

The literature on how mTBI and co-morbid PTSD affect each other and the effects on Veterans several years post-deployment is sparse. Treatment recommendations specific to Veterans with both mTBI and PTSD are in flux, and while treatments address each disorder independently, they may not be effective when the two disorders co-occur. Further impacting successful treatment of Veterans is the fact that many Veterans do not seek treatment, in part due to the distance they travel to obtain VA services and stigma.

Treatments that are accessible and improve symptoms in patients with mTBI and PTSD alone may facilitate rehabilitation in Veterans with co-morbid mTBI and PTSD. Meditation has been suggested to be effective in Veterans with PTSD and in civilians with TBI, improving quality of life. The current study proposes a type of meditation targeted for Veterans, Inner Resources for Veterans (IRV).

Inner Resources for Veterans (IRV) meditation intervention is based on Inner Resources for Stress, an intervention which utilizes mindfulness, techniques that encourage non-judgmental attention to oneself in the present moment. The Inner Resources protocol targets PTSD and has been associated with reduced PTSD and anxiety symptoms, reduced number of depressive symptoms, and depression remissions at a 9-month follow-up, as well as increased perceived self-efficacy. Pilot results of older combat Veterans with PTSD indicated that Inner Resources is a safe, feasible, and acceptable intervention for this population. In a previous study with IRV in veterans at the Michael E. DeBakey VA, the control condition provided education on the symptoms and effects of PTSD. For example, subjects learned to recognize the circumstances that triggered their symptoms, how to identify and participate in healthy activities, and how to monitor their sleep.

In addition to the changes in functional and psychological symptoms and neural pathways, IRV would offer Veterans a treatment they could utilize whenever challenging situations occur regardless of location. Since the treatment would be relatively cost-free after initial training, IRV could also dramatically reduce financial burden to both Veterans and VA. Few treatment studies focusing on Veterans with co-morbid mTBI and PTSD support the innovation of this study, as does generation of community integration data to relate to changes in functional connectivity.

## **Section D: Purpose and Objectives**

Aim. Investigate effects of a meditation intervention designed for Veterans (Inner Resources for Veterans; IRV) on three aspects of rehabilitation in Veterans with both mTBI and PTSD:

Hypothesis 1 (Rehabilitation of Community Integration and Quality of Life): Veterans participating in IRV, relative to an Education Control (EC) group, will exhibit improvements in community reintegration and quality of life after eight weeks of treatment.

Hypothesis 2 (Rehabilitation of Psychological Symptoms): Veterans participating in IRV, relative to an [(EC)] group, will exhibit improvements in PTSD and postconcussive symptoms after eight weeks of treatment.

Hypothesis 3 (Rehabilitation of Neural Networks): Following IRV, functional connectivity in the IRV group will be normalized, e.g., relative to the EC group, Veterans in the IRV group will demonstrate reduced Default Mode Network resting state functional connectivity with lateral prefrontal cortex (LPFC), and increased resting state functional connectivity between the rostral anterior cingulate and amygdala after eight weeks of treatment.

## **Section E: Protocol Risks/Subjects**

### **E1. Risk Category**

Category 1: Research not involving greater than minimum risk.

### **E2. Subjects**

Gender:

Both

Age:

Adult (18-64 yrs)

Ethnicity:

All Ethnicities

Primary Language:

English

Groups to be recruited will include:

Patients

Which if any of the following vulnerable populations will be recruited as subjects?

Mentally ill

Vulnerable populations require special protections. How will you obtain informed consent, protect subject confidentiality, and prevent undue coercion?

The subjects recruited for the study will be informed of the purpose of the study and the procedures involved. When the researchers explain the experimental procedure and detail any potential risk factors associated with filling out questionnaires, completing the diagnostic interviews, and being inside a Magnetic Resonance Imaging (MRI) scanner, they will be careful to ask if there are any questions and to ask questions to indicate if they are being understood. Participants will be informed that they are under no obligation to participate and that they can discontinue their involvement in the study at any time without penalty. They will be assured that their treatment will in no way be affected by their choice to participate or not to participate, or their choice to withdraw at any time. Only patients who have the cognitive and legal ability to give informed consent for themselves, without a legal

guardian or Legally Authorized Representative, will be included. Much of the study procedures are conducted by mental health professionals who are sensitive to the needs of mental health patients, and they will incorporate those skills into the study procedures, e.g., when subjects fill out assessment questionnaires.

### **E3. Pregnant woman/fetus**

Will pregnant women and/or fetuses (as described in 45 CFR 46 Subpart B) be enrolled in the research?

No

### **E4. Neonates**

Will neonates of uncertain viability or nonviable neonates (as described in 45 CFR 46 Subpart B) be enrolled in the research?

No

### **E5. Children**

Will children be enrolled in the research?

No

## **Section F: Design/Procedure**

### **F1. Design**

Select one category that most adequately describes your research:

c) Pilot

Discuss the research design including but not limited to such issues as: probability of group assignment, potential for subject to be randomized to placebo group, use of control subjects, etc.

This is a prospective, randomized, controlled, single-blinded intervention study. Subjects will be randomized to either the IRV Meditation group or the Education Control group and have a 50% chance of being in either group.

#### Inclusion Criteria:

All subjects will meet the following inclusion criteria: 1. Mild traumatic brain injury (mTBI) as defined by the VA/DoD Clinical Practice Guideline. 2. PTSD as assessed by the Clinician Administered PTSD Scale (CAPS); 3.

Aged 18 - 49; 4. Have been referred for treatment by a clinician at the MEDVAMC; 5. Have not previously participated in meditation training.

#### Exclusion Criteria:

We will exclude subjects who: 1. Meet DSM-IV criteria for drug or alcohol abuse in past 30 days; 2. Have a history of severe TBI based on any of following: (i) Glasgow Coma Score < 8; (ii) alteration of consciousness greater than 24 hours; loss of consciousness greater than 30 minutes; 3. Have current neurological or general medical conditions known to impact cognitive and/or emotional functioning, including but not limited to: epilepsy, Parkinson's disease, Huntington's disease, Alzheimer's disease, stroke, chemotherapy for cancer; 4. Have acute psychological instability as assessed by MEDVAMC clinician or study staff or concurrent diagnosis or

schizophrenia, schizoaffective disorder, delusional disorder, organic psychosis, and subjects taking antipsychotic medication, and 5. Have already completed a course of meditation training.

We may also exclude participants with general contraindications for MRI, including metal in or around the head (e.g., orthodontia, non-removable body piercings, etc.), ferromagnetic material in the body (e.g., non-removable body piercings), or non-MRI compatible medical devices.

## **F2. Procedure**

### Overall

Subjects will attend consent and assessment visits prior to being placed in the Inner Resources for Veterans (IRV) meditation intervention or education control (EC) groups. Before beginning the group and group completion, subjects will also undergo MRI.

### Consent

The subjects recruited for the study will be informed of the purpose of the study and the procedures involved. When the researchers explain the experimental procedure and detail any potential risk factors associated with filling out questionnaires, completing the diagnostic interviews, and being inside a Magnetic Resonance Imaging (MRI) scanner, they will be careful to ask if there are any questions and to ask questions to indicate if they are being understood. Participants will be informed that they are under no obligation to participate and that they can discontinue their involvement in the study at any time without penalty. They will be assured that their treatment will in no way be affected by their choice to participate or not to participate, or their choice to withdraw at any time. Only patients who have the cognitive and legal ability to give informed consent for themselves, without a legal guardian or Legally Authorized Representative, will be included.

### Assessments

Pretreatment Assessment: Consented Veterans will then participate in a pretreatment assessment sessions that will consist of clinician administered and self-report instruments (e.g., the Structured Clinical Interview for DSM-IV Axis-I Disorders (SCID-I; Steiner et al., 1988; Shear et al, 2000); the Clinician-Administered PTSD Scale (CAPS; Blake et al., 1995; Weathers et al. 2001); the Beck Depression Inventory II (BDI-II; Beck et al., 1996); the PTSD Check List (Weathers et al., 1993); the Neurobehavioral Symptom Inventory (NSI), Trust Inventory, Trail-making task, and Rey Auditory Verbal Learning Test). Information on alcohol and drug use may be asked on the SCID or other form. These questionnaires will take approximately 2.5 hours for subjects to complete. Prior to beginning the interview, subjects will be informed that some of the questions are personal in nature, and that some of the questions may cause them to become upset, particularly PTSD participants when discussing their experiences. In addition, subjects will be reminded that they may take a break whenever necessary and can discontinue the questionnaires if they feel they need to.

Posttreatment Assessment: Approximately two weeks following the final treatment session, participants will complete a posttreatment assessment with a member of the study staff. The measures administered in this assessment will consist of those measures completed in the pretreatment assessment, with the addition of surveys designed to assess participants' therapy experience, e.g., the Client Satisfaction Questionnaire (CSQ).

Follow-up Assessment: Approximately eight weeks after the Posttreatment Assessment, participants will complete a Follow-up assessment with a member of the study staff. The measures administered in this assessment will consist of those measures completed in the pretreatment assessment.

### Group Assignment

Following the assessment phase, participants will be randomized to either the IRV or EC group. The IRV intervention is a manualized meditation intervention that consists of eight 90-minute group sessions. The first third of each session is spent learning and practicing meditation techniques, the middle third on didactic material and group discussion, and the last third practicing meditation and debriefing. Outside of the sessions, subjects

practice approximately 30 minutes a day for 6 days per week. The Education Control group will cover material on PTSD (e.g., the causes, symptoms, and treatment) and will be held in sessions of similar duration.

#### Pre- and post-treatment fMRI Scans

Before beginning and approximately 12 weeks after completing the IRV intervention or EC groups, participants will be invited to participate in an MRI scan. Study staff will review safety issues related to MRI with the subject and answer any questions. The MRI scanner we will use is a conventional 3.0 Tesla scanner that has been approved for clinical use by the FDA. A mental health provider or trained study staff with experience working with psychiatric populations will be present in the scanner control room throughout the experiment for immediate availability if the patient becomes agitated or frightened. In an effort to reduce the possibility that subjects will be adversely affected by the scanner noise or the appearance of visual stimuli, subjects may be acclimated to the scanner by being permitted to enter it prior to the scan to become familiar with the sounds and enclosed space of the scanner. These habituation procedures have been very successful in terms of stress and movement reduction. Veterans will be informed that if they do not complete the entire scan, they will still be compensated. Should the participant indicate at any time that they choose to discontinue the study, the study will be terminated at no penalty to the subject. Subjects who potentially have metal in their bodies but are not sure, e.g., subjects with a history of welding, will be asked to undergo x-ray in order to identify whether there is metal in their bodies. A radiologist will be asked to review the MRI scans of the subjects and provide reports of his review as a courtesy to the subjects.

#### Treatment Adherence and Fidelity

Treatment adherence will be assessed by session attendance, recorded at all sessions on the Session Attendance Form, and by the proportion of the recommended 180 minutes per week of meditation practice that each Veteran reports. The IRV Daily Practice Log will be completed for all 8 weekly sessions.

Project Therapists will audio-record all sessions using a digital recorder. These recordings will be stored consistent with MEDVAMC privacy and security requirements. Project Therapists will have weekly 1-hour phone supervision with [name], developer of IRV, to insure treatment fidelity. Approximately 20% of the taped sessions will be assessed for fidelity using fidelity measures provided by an expert IRV Therapist ([name]).

All research data is stored as de-identified data with their coded study ID. We maintain a master list of the name of Veterans who participate in the study and their coded study ID. This list is stored separately from the research data and is only accessible by the study staff.

There will be no administration of drugs or placebos or other treatments in any of the visits.

The health records of participants will be flagged to indicate they are in an interventional study that could possibly affect other medical care.

## Section G: Sample Size/Data Analysis

### G1. Sample Size

How many subjects (or specimens, or charts) will be used in this study?

Local: 60      Worldwide: 60

Please indicate why you chose the sample size proposed:

In a meditation study with Veterans that used mantra repetition, a component of IRV, reductions in Posttraumatic Stress Disorder Checklist total scores showed a moderate-to-large effect size, Cohen's  $d=0.72$  (0.2 is small, 0.5 is moderate, 0.8 is large). A study of loving kindness meditation with Veterans with PTSD reported a large effect size ( $d=0.89$ ) at a three month post-intervention follow-up. A third meditation study also with Veterans from other

war eras with PTSD showed large effect sizes on CAPS in both Intent to Treat (ITT) (Cohen's  $f=0.42$ , approx. equal to  $d=0.84$ ) and completer analyses ( $d=1.24$ ). We more conservatively assume an effect size of  $d=0.63$ . At a significance level of 0.05, with 40 patients (20 patients in each group) we will have power of 0.8 to detect the moderate to large effect size of 0.63. Assuming an attrition rate of 33%, 30 subjects are proposed in each group.

Functional Connectivity MRI Power Analysis (Hyp. 3). In the model that power analysis for fMRI SPM Random Effects Analysis was based on, brain signals are modeled by continuously distributed Gaussian kernels of random height and of width,  $f$ , in proportion to  $W$ , where  $W$  is the smoothness of the random field in units of voxels. Based on the pilot fcMRI data, with effect size of  $d = 0.70$ , observed  $W$  equivalent to [4.9 4.8 4.7] voxels FWHM, observed  $S = 2023$  resels, observed  $f = 2.72*W$ ,  $u = 3.167$ , calculated 2-tailed FWE-corrected cluster  $k_{\alpha}$

$(0.05) = 183$  voxels, shows that a power of 0.82 would be achieved by 20 subjects per group (after attrition). It should be also be noted that cluster sizes greater than this were observed in our fcMRI pilot data.

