## G2. Data Analysis

Provide a description of your plan for data analysis. State the types of comparisons you plan (e.g. comparison of means, comparison of proportions, regressions, analysis of variance). Which is the PRIMARY comparison/analysis? How will the analyses proposed relate to the primary purposes of your study?

All analyses will be done on an intention-to-treat basis, indicating that all randomized participants and all outcomes will be included in the analysis according to their assigned treatment groups regardless of their adherence to their assigned treatment or their purported relationship to the treatment. Baseline Analysis: Imbalance in groups may occur by chance; we will examine baseline characteristics (e.g., age and psychotropic medication) of participants randomized to the two groups. Chi-square and t-tests will be used to evaluate the differences between groups for categorical and continuous variables, respectively.

Behavioral Outcome Analyses (Hypotheses 1-2). For all outcomes, we will examine the normality of the

distribution of the variable to determine if transformations such as log or inverse might be needed. In order to control for type I error due to multiple comparisons on multiple tests, we will use a rank sum scoring approach. There will be one rank sum score variable for the CAPS (primary outcome measure), and one for psychological tests (secondary outcome measures). The primary analysis is to assess the meditation effect, for which we will use a general linear mixed model, containing terms of treatment, time period, and interaction between time and treatment. The treatment effect will measure differences between the intervention and control groups at baseline, and the time effect will measure whether there was an overall change over time in the outcome. The term of most interest will be the interaction between time and treatment. A secondary analysis will include covariates of age and medication usage Method for Missing data: Because a research assistant verifies completion of each item, missing data are anticipated to be low. We assume any missing data will be missing at random, which can be indirectly verified by comparing the distribution of other important measures between patients with and without complete data. We will apply multiple imputation methods on the missing data and impute the missing data 20 times.

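### The stated power of 0.8 for d = 0.63 with 20 patients per group does not follow from the inputs given; a two-group test has power 0.49 (two-sided)

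*Combined protocol and SAP*

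**What the plan says.** G1 assumes d = 0.63, described as conservative against three cited meditation studies. At a significance level of 0.05 it states that "with 40 patients (20 patients in each group) we will have power of 0.8 to detect the moderate to large effect size of 0.63". It then inflates for dropout: "Assuming an attrition rate of 33%, 30 subjects are proposed in each group". The 20 per group are therefore completers, and the fMRI paragraph of G1 uses the same number: "a power of 0.82 would be achieved by 20 subjects per group (after attrition").

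The analysis that this power has to serve is in G2 (Data Analysis): a linear mixed model with treatment, time and their interaction. There, "The term of most interest will be the interaction between time and treatment", while "The treatment effect will measure differences between the intervention and control groups at baseline". The primary outcome is a rank sum score for the CAPS. For incomplete data, "We will apply multiple imputation methods on the missing data and impute the missing data 20 times".

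Under F2, Assessments, there are two post-baseline visits. One is about two weeks after the last session, and then "Approximately eight weeks after the Posttreatment Assessment, participants will complete a Follow-up assessment with a member of the study staff". Section D frames Hypotheses 1 and 2 as improvement relative to the education control after eight weeks of treatment.

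**The concern.** With 20 per group, a two-group comparison usually needs d close to 0.9 for 80% power, so 0.8 at d = 0.63 looks too high. A repeated-measures analysis can do better than a simple comparison, but only through a contrast and a correlation that G1 does not mention.

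F1 classes the study as a pilot, but G1 still justifies the 60 subjects by this figure. As written, it implies a 20% chance of missing d = 0.63. If the real chance is nearer one half, a null result on CAPS will be read as more informative than it is.

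**Working it through.** **Inputs.** From G1: d = 0.63, level 0.05, 20 evaluable per group, attrition 33%. From F1: 1:1 allocation. From G2: time-by-treatment interaction. From F2: one baseline and two post visits. Not given: test, sidedness, SD for d, contrast, correlation. Two-sided testing is my base case.

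**1. The plan's figure as a two-group test.** Noncentral t with 2n − 2 df and noncentrality d·√(n/2). For n = 20 this is 0.63 × √10 = 1.99 on 38 df, against a critical value of 2.02.

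| n per group | Two-sided | One-sided | d detectable at 80%, two-sided |
|---|---|---|---|
| 20 | 0.493 | 0.622 | 0.91 |
| 30 | 0.670 | 0.778 | 0.74 |
| 40 | 0.795 | 0.875 | 0.634 |
| 41 | 0.805 | 0.882 | – |

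The stated 0.8 is not reproduced at 20 per group. It is reproduced at 40 in each group, where the detectable d also rounds to 0.63.

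**2. The planned interaction, d standardised on the change.** Assume equal correlations across visits and the same effect at both post visits.

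- One post visit: a t-test on change with d = 0.63, so power 0.493.
- Two post visits averaged: in raw-score variance units a single change has variance 2(1 − r) and the averaged change 1.5(1 − r). The effective d is 0.63 × √(2/1.5) = 0.727. Power is 0.611 (one-sided 0.730).
- Joint 2-df test: noncentrality n·d²·(2/3) = 20 × 0.3969 × 0.667 = 5.29 on 2 and 76 df. Power is 0.511.

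Simulation of 40,000 trials gave 0.489 for one post visit and 0.606 for the average. A separate simulation of 20,000 trials gave 0.513 for the joint test.

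With complete data on all 30 per group the powers are 0.670, 0.791 and 0.702 in the same order. At 20 per group, the d detectable with 80% power is 0.91, 0.79 and 0.87.

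**3. The planned interaction, d in raw-score SD units.** Divide d by √(2(1 − r)) for one post visit or √(1.5(1 − r)) for the average. For the joint test, noncentrality is n·d²/(3(1 − r)). Two-sided, 20 per group:

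| Contrast | r = 0.5 | r = 0.6 | r = 0.7 | r needed for 0.80 |
|---|---|---|---|---|
| One post visit | 0.49 | 0.58 | 0.71 | 0.76 |
| Two averaged | 0.61 | 0.71 | 0.82 | 0.68 |
| Joint 2-df | 0.51 | 0.61 | 0.74 | 0.74 |

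One-sided, the needed r falls to about 0.69 (one post visit) and 0.59 (two averaged).

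**4. Other routes to about 0.8.**

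- Repeated-measures formula with f = d/2 = 0.315 (G1 equates f = 0.42 with d = 0.84), N = 40, two visits, r = 0: noncentrality 0.315² × 40 × 2 = 7.94, power 0.784. In a 2 × 2 interaction, f is the difference in change divided by 4, in SD units. So f = 0.315 means 4 × 0.315 = 1.26 SD, twice 0.63.
- Single-group pre-post test, n = 20: noncentrality 0.63 × √20 = 2.82. Power is 0.804 by normal approximation and 0.762 by exact t. It makes no comparison with the control group.

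**5. Attrition.** 20/0.67 = 29.9, which rounds to 30. This step is correct.

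**The case against.** The strongest reply is that G1 is under-specified rather than wrong. It does not say that d is standardised on the change, and a raw-score d with a high enough correlation gives 0.80. The hypotheses are directional, and one-sided testing lowers the correlation needed. A baseline-adjusted average of the two post visits, with d in raw-score units, would have two-sided power of 0.74 to 0.83 for correlations of 0.3 to 0.6. This stands as far as it goes: 0.8 is attainable with added inputs. But none of them is in the plan, and the G2 model estimates a baseline group difference rather than adjusting for baseline.

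The 0.61 is itself conditional. If the post visits correlate 0.8 with each other and 0.5 with baseline, it falls to 0.535; if they correlate 0.3 with each other, it rises to 0.67. None of these calculations allows for the rank sum scoring of the outcome.

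It can also be said that intention-to-treat analysis uses all 30 per group, where the averaged contrast has power 0.79. That needs complete data on everyone. With a third lost, multiple imputation does not restore the full information, so 0.79 is an upper limit under those assumptions.

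Finally, the per-group reading of 40 is only one possible cause, since a single-group calculation also comes close. It is something for the sponsor to check, not a finding.

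**Conclusion.** The concern holds. The stated 0.8 does not follow from the inputs in G1: a two-group test gives 0.49 two-sided and 0.62 one-sided.

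For the planned interaction, two-sided power is 0.49 to 0.61, provided that d is standardised on the change, correlations are equal and the effect is the same at both post visits. On the one-post-visit contrast, the chance of missing d = 0.63 is about 51% with 20 completers per group, and about 33% at best if all 30 per group were analysed with full information. For 80% power, that contrast would need 41 evaluable per group.

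The conclusion about the stated figure does not depend on how the error arose. The true power of the planned analysis cannot be settled until the sponsor states the SD, contrast and correlation.

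**What to change.** Enrolment can stay as it is.

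1. In G1, state the test, sidedness, standardising SD, interaction contrast and assumed correlation behind 0.8. Check whether 40 was a per-group number.
2. Give power over a range of correlations for the chosen contrast, as in the table under step 3 of the working.
3. If no supporting assumption was made, replace the sentence with text such as:

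> With 20 completers per group and two-sided alpha 0.05, power to detect a between-group difference of d = 0.63 in change from baseline to post-treatment (d standardised on the change) is about 0.49; 80% power is available for d of about 0.91.

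This replacement describes the post-treatment contrast, which fits the hypotheses in Section D. If the sponsor settles on a contrast using both post visits, the corresponding figures (0.51 joint, 0.61 averaged, under the stated assumptions) should be used instead.

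The cost is protocol wording only. The stated power becomes less favourable unless the sponsor can document a contrast and correlation that support 0.80.
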